 - H1a. The percentage of MI interviews in the first 40 consecutive, study-eligible inpatients identified by the research team will be higher in the "DO ONE" than "SEE ONE" group;
 - H1b. The percentage of MI interviews in the first 40 consecutive, study-eligible inpatients identified by the research team will be higher in the "ORDER ONE" than "SEE ONE" group.
2. To assess the integrity of MI when Healthcare providers use it on the medical units.
 - H2a. DO ONE will result in more proficiently conducted MI sessions than SEE ONE;
 - H2b. ORDER ONE will result in more proficiently conducted MI sessions than SEE ONE.
3. To assess the cost-effectiveness of the three strategies.
 - H3a. SEE ONE will be the most cost-effective implementation strategy when the threshold value to decision makers of inpatients receiving an additional MI session to a criterion level of adequate performance is relatively low;
 - H3b. DO ONE and ORDER ONE will be more cost-effective than SEE ONE when the threshold value is relatively high.

The primary outcome for MI *uptake* will be the percentage of MI sessions conducted for study-eligible inpatients as verified by audio recordings. For MI *proficiency*, primary outcomes will be 1) independently rated MI adherence and competence ratings of the sessions, and 2) the percentage of sessions achieving a criterion level of adequate MI performance used in MI effectiveness¹⁸⁻²⁰ and clinician training trials.^{21,22} In addition, we will calculate the relative costs and cost-effectiveness of the three MI implementation strategies. Secondary outcomes across the three conditions will be 1) independently rated strength and frequency of patient statements that favor change in the sessions (called change talk) as a proxy for patient outcomes,^{23,24} and 2) themes related to implementation facilitators and barriers identified through qualitative assessment.

2. **Background:** Describe the background information that led to the plan for this project. Provide references to support the expectation of obtaining useful scientific data.

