The proposed project will evaluate the effectiveness of three different implementation strategies for integrating MI into the YNHH's internal medicine hospitalist service and other general medical inpatient units. Specifically, we will randomize 30 Healthcare providers to one of three conditions: (1) a continuing medical education workshop that "shows" the healthcare providers MI (the control condition, referred to as SEE ONE); (2) a 'see one, do one' apprenticeship model involving workshop training plus live supervision of bedside practice (DO ONE); and (3) ordering MI from CL after learning about it in a workshop (ORDER ONE). After receiving the respective MI training, each Healthcare provider will be followed for provision of MI to study-eligible/consented patients. In ORDER ONE, healthcare providers may elect to conduct MI themselves or order it to be conducted by Psychiatrists from the CL service.

After the Healthcare providers have attended their respective workshops, research staff will identify substance using patients in need of a MI intervention. Research staff will independently screen, assess and obtain consent from eligible patients who are admitted to the internal medicine hospitalist service and other general medical inpatient units. Patients will be potentially included if they are assigned to a participating Healthcare provider according to the hospital's usual clinical administrative procedures. Thus, patients will follow the randomization condition of their Healthcare provider, though Healthcare provider will not know which patients on their caseloads have enrolled in the study. This approach will permit a naturalistic test of the Healthcare provider's ability to identify and intervene using MI with patients who have substance use problems. Each Healthcare provider will be followed until he or she has

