General medical inpatient units have a patient population characterized by very high rates of co-morbid substance use disorders typically in excess of rates found in other primary care settings.¹ Moreover, large numbers of hospitals have adopted the hospitalist model for inpatient care on medical units,¹⁰⁹ and almost all hospitals have psychiatric CL services for addressing mental health and addiction problems that fall outside the expertise of medical providers.^{17,110} This study has the potential to identify highly disseminative strategies for integrating substance abuse services into primary care in a major sector of the U.S. health care system.

The practice under study for implementation is a single 20-min MI session that we have used to train medical students and physicians^{21,89} and are currently comparing to a computerized MI approach with substance using women in outpatient primary care treatment.⁸⁷ The MI session includes six steps: (1) understand patient's view of his/her substance use and motivations for change; (2) discuss reasons for using vs. not using/cutting down; (3) provide personalized feedback about patient's substance use; (4) continue handling resistance skillfully and draw out change talk; (5) develop a change plan or present change options for later consideration; and (6) summarize and support what the patient has decided to do. Clinicians ask key questions at the conclusion of steps 2-4 to ascertain the patient's commitment to change. If the patient endorses a goal of quitting or cutting back substance use, the clinician immediately proceeds to Step 5. Thus, clinicians adapt MI to their specific patient's readiness to change, giving the manualized treatment flexibility to avoid a rigid application of MI that might undermine its effectiveness and acceptability to clinicians.^{24,46}

Healthcare providers will each receive the MI implementation strategy offered within their assigned condition. Separate workshop trainings will occur for Healthcare providers within conditions. Additional workshops will be conducted as needed if new Healthcare providers are recruited into the study. In each condition, all Healthcare provider as well as the Psychiatrists from CL in ORDER ONE will audio record their MI interviews to confirm the interviews have occurred and to permit MI integrity rating.

1. Workshop (See One)

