Healthcare providers in this condition will participate in a 1-day skill-building workshop. [name], a member of the Motivational Interviewing Network of Trainers (MINT) and a highly experienced MI workshop trainer, will conduct the workshop per MINT recommendations, giving the Healthcare providers an opportunity to "see" the MI intervention and learn how to conduct it through expert and

video demonstrations and experiential activities. He also will teach the Healthcare providers how to screen patients for risky substance use with NIAAA Guidelines, the CAGE Questionnaire and Heaviness of Smoking Index¹¹⁴ (described below). A 2-hr “booster” session will be provided to Healthcare providers once they have reached their halfway point of the trial phase (20 eligible patients), consistent with the common practice of requiring annual refresher training for critical procedures used by staff in hospitals.

2. Workshop plus live supervision (Do One)

Healthcare providers will participate in a 1-day skill-building workshop conducted by [name], including halfway point booster sessions, as outlined above. Following the workshop, the Healthcare providers will each “do one” MI intervention under the live supervision of a Psychiatrist from CL. [name] will have taught the CL psychiatrists to conduct MI and will have trained them in the supervisory practices developed in our prior MI training work (See Appendix B).^{21,89,90} Healthcare providers can request additional live supervision at any point during the trial, consistent with the apprenticeship model.¹³⁻¹⁶ Additionally, once the Healthcare provider in this condition reaches their halfway point of the trial phase (20 eligible patients), they will be offered another bedside supervision as a refresher of their MI skills.

3. Workshop plus consultation-liaison service (Order One)

Healthcare providers will participate in a 1-day skill-building workshop and annual booster sessions conducted by [name]. The Healthcare providers in this condition will be instructed that they may either administer MI or they may “order” a MI interview to be delivered by a Psychiatrist from CL with specialty MI training. This is the only group that may “order” a MI interview.

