Before Healthcare providers can “order” MI from CL, [name] will train and supervise the CL Psychiatrists in MI, who will provide adequate coverage for administration of MI during the data collection period of the project. Training will follow a clinical trials training approach used in efficacy and effectiveness trials:^{115,116} 1) a 2-day skill-building workshop; 2) three post-workshop supervised practice cases based on review of audio recorded sessions using the NIDA-SAMHSA MI supervision blending product, MIA: STEP,^{86,94}; and 3) follow-up monthly individual supervision to maintain and monitor the CL experts’ MI practice.

4. Rationale for implementation strategy choice and study design

Continuing medical education workshop/seminar training plus booster sessions is the usual approach for teaching medical professionals new or unfamiliar clinical practices^{70,71} and will serve as our control condition. By holding this training constant across conditions, we can isolate the effects of live-supervision in DO ONE and ability to order MI from CL in ORDER ONE that exceed those which occur in primary care training-as-usual efforts. We considered a two cell design that would compare DO ONE and ORDER ONE. However, to our knowledge neither DO ONE or ORDER ONE have been tested in primary care settings. Given this, we felt that a true “control condition” by which to compare uptake, MI proficiency, and cost effectiveness is required.

5. Rationale for sample choice:

We are recruiting a heterogeneous sample of substance using patients to test the implementation strategies in clinical circumstances typically seen by Healthcare providers on general medical inpatient units. Finally, most Healthcare providers and all MI integrity raters are mono-lingual English speakers. We therefore do not have the capacity to include Spanish-only speaking patients in the study.

G. Procedures for monitoring Healthcare provider-patient assignments and audio recording MI interventions

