
All Healthcare providers and Psychiatrists from CL will be issued a digital recording device. They will audio record their own MI sessions and personally consent patients for such recordings and give the recordings to the research assistant, along with identifying information that will enable the research assistant to check the patients' study enrollment status. If recordings are obtained from non-study participants (e.g., someone that was deemed ineligible or who did not provide consent), they will be immediately erased. Otherwise, they will be downloaded for storage on a secure server for later analysis.

As part of a research assistant's job, he or she will regularly send messages to all of the Healthcare providers reminding them to record any MI interventions (or CL referrals) they conduct with patients on the unit. As a back-up, additional recording devices will be conveniently placed on the units, and the administrative assistant on the CL service and research assistants will have additional recording devices that can be given to Healthcare providers and Psychiatrists from CL on demand. [name] and [name] will be apprised of the overall success of obtaining audio recorded MI interviews, although they will not be told of the success for each of the Healthcare providers or their assigned conditions. They will assist with compliance for obtaining recorded sessions if there are problems.

H. Assessments:

Data will be collected by self-report, interview questionnaires and audio recordings. The Healthcare providers will complete structured questionnaires and qualitative interviews. All of this will be coded by a subject ID rather than the individual's name. Similarly, the audio recordings will be stored as computer files on a secure server and only include subject IDs to label the interview.

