- *Evaluation of effects at implementation strategies:* The principal strategy for assessing the effectiveness of the study implementation conditions on outcome will be mixed effects general linear models for continuously measured primary (e.g., MI integrity) and secondary (e.g., strength and frequency of patient change talk) outcomes variables, and generalized linear mixed models for binary outcomes (e.g. meets criterion MI performance threshold). In both types of models we will have training condition as the main predictor variable and will include random effects for Healthcare providers to account for clustering of observations within Healthcare providers. Our main hypotheses involve group comparisons with the SEE IT group as the reference condition. We will consider significant comparisons of the DO IT and ORDER IT conditions to the SEE IT condition as supportive of our hypotheses. Comparisons of DO IT with ORDER IT will be conducted for exploratory purposes only.

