- *Adequacy of sample size for primary hypotheses:* Effect sizes for power estimation for the continuous outcomes were based on studies by Miller et al.²³ (d=0.4 to 0.8) and [name] et al.²¹ (d=0.4 to 1.2). A review article by Apodaca and Longabaugh¹⁴⁸ also suggests that at least medium effect sizes are expected for the between-group comparisons. [name] et al.²¹ observed large effect sizes for the binary outcome comparison (meets criterion MI performance threshold, 53% vs. 18%); however, we conservatively assume a medium effect size for this comparison as well. Intra-class correlations accounting for expected within clinician variance were estimated based on Imel et al¹⁴⁹ and are expected to be small (in the 0.05 to 0.10 range). Feasibility constraints (i.e., 10 Healthcare providers per condition) limited the number of clusters (Healthcare providers) that we could consider. Finally, because we do not expect all Healthcare providers to identify substance using patients and use MI with them (i.e., our 1st hypothesis about MI uptake), we will require a larger sample size of study-enrolled patients to reach our targeted number of audio recorded MI sessions for hypothesis testing purposes. We estimate 80% of patients across conditions will receive MI. Based on these estimates and constraints, alpha level of 0.05 and power of 80%, 30 Healthcare providers and 40 patients per Healthcare provider will be sufficient for testing the primary hypotheses of the study. Table 2 shows the actual total sample size for the cluster-randomized design for continuous and binary outcomes, adjusted for a conservative estimate of MI uptake.

Table 2: Sample size estimates for the primary aims of the study based on alpha=0.05 for the pairwise comparisons of each condition to the control condition and 80% power.

Effect size	Total sample size for an ordinary RCT (3 arms)	ICC	Number of Healthcare provider	Average number of patients per Healthcare provider	Total sample size for a cluster RCT unadjusted for estimated MI uptake	Total sample size for a cluster RCT adjusted for estimated MI uptake
d=0.4	300	0.07	31	31	930	1116
40% vs 18%	195	0.1	30	17	510	765

3. Incremental cost-effectiveness analyses

The relative cost-effectiveness of the three MI implementation strategies will be assessed using both incremental cost-effectiveness ratios (ICERs) and cost-effectiveness acceptability curves (CEACs).

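### ORDER ONE sessions may be run by shared CL psychiatrists, but the models cluster only by provider, so the H2b standard error can be too small

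*Combined protocol and SAP*

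**What the plan says.** Section V, item 12, *Evaluation of effects at implementation strategies*, plans linear mixed models for continuous outcomes and generalized linear mixed models for binary ones. Training condition is the main predictor, and the models "will include random effects for Healthcare providers to account for clustering of observations within Healthcare providers". No other clustering term is given.

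H2b, under the Primary Aims, is: "ORDER ONE will result in more proficiently conducted MI sessions than SEE ONE". Its outcomes are the ITRS adherence and competence means and whether a session meets the adequacy criterion. All of these rate the person conducting the session.

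In SEE ONE and DO ONE that person is the randomised provider. In ORDER ONE, "healthcare providers may elect to conduct MI themselves or order it to be conducted by Psychiatrists from the CL service" (item 3, *Research Plan*). The *Order One* description adds that the provider may request an "MI interview to be delivered by a Psychiatrist from CL with specialty MI training". These sessions count: "all Healthcare provider as well as the Psychiatrists from CL in ORDER ONE will audio record their MI interviews", partly so that integrity can be rated.

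The psychiatrists are described only as a group "who will provide adequate coverage for administration of MI during the data collection period of the project". Their number, the expected ordered share and any pairing of psychiatrists with providers are not stated. The *Study Setting* section describes CL orders arriving through the electronic record and being seen by CL staff in general.

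The sample size text also treats providers as the only clusters: "Feasibility constraints (i.e., 10 Healthcare providers per condition) limited the number of clusters (Healthcare providers) that we could consider".

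**The concern.** The text consistently lists the CL psychiatrists separately from the healthcare providers, so the provider random effect cannot be read as covering them. When one psychiatrist takes orders from several providers, that psychiatrist's skill enters the session scores of all of them. This has two effects:

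- The ORDER ONE mean carries a variance component that does not shrink as providers or sessions are added. It shrinks only with more psychiatrists.
- Provider means within ORDER ONE become more alike, so the between-provider variance that the model estimates falls just when the true uncertainty rises.

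A chance difference in skill among a few psychiatrists could then be reported as an effect of the ordering strategy. Change talk, a secondary outcome that the Background ties to clinician proficiency, is probably affected too, but this was not quantified. The check covers H2b only; nothing is claimed about H1a, H1b or H2a.

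**Working it through.** **Inputs from the documents.** Ten providers per arm, three arms, two-sided 5% level, d = 0.4, ICC 0.07 for the continuous row of Table 2 and 0.10 for the binary row (text range 0.05 to 0.10). Forty patients per provider at 80% uptake gives 40 × 0.80 = 32 sessions.

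**Assumed, because not given.** Number of psychiatrists K, share q of ORDER ONE sessions that are ordered, and psychiatrist variance (equal to or half the provider variance). Orders are spread over psychiatrists at random. A provider's own effect enters only the sessions that provider conducts.

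**Step 1: the plan's own figures.** With design effect 1 + (m − 1) × ICC, 300 × (1 + 30 × 0.07) = 300 × 3.1 = 930, as stated. For the binary row, 195 × (1 + 16 × 0.10) = 195 × 2.6 = 507, shown as 510 = 30 × 17. Clustering is therefore by provider alone.

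**Step 2: no ordering.** SE of the arm difference = √[2 × (0.07 + 0.93/32)/10] = √0.01981 = 0.141. Simulated type I error is 5.0%, with 78% power at d = 0.4. The planned model is sound here.

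**Step 3: with ordering.** In total-SD units, with equal variances:

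- Var(ORDER ONE mean) = (1 − q)² × 0.07/10 + q² × 0.07/K + 0.93/320
- Var(SEE ONE mean) = 0.07/10 + 0.93/320 = 0.00991

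A provider-only SE omits the middle term of the first line. For q = 1 and K = 3:

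- correct: √(0.02333 + 0.00291 + 0.00991) = 0.190
- omitting the term: √(0.00291 + 0.00991) = 0.113, a ratio of 1.68

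For K = 3 the ratio is 1.41 at q = 0.75, 1.18 at q = 0.5 and 1.04 at q = 0.25. For q = 1 and K = 10 it is 1.24.

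**Step 4: the planned test, continuous score.** The model pools provider variance over three arms (30 − 3 = 27 df), which softens the ratio slightly. Type I error for H2b over 40,000 null trials per cell:

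| Psychiatrist variance | Share ordered | K=2 | 3 | 4 | 6 | 10 | 20 |
|---|---|---|---|---|---|---|---|
| Equal | 100% | 26.5% | 19.8% | 16.1% | 12.0% | 8.6% | 5.8% |
| Equal | 50% | 9.8% | 7.9% | 6.8% | 5.8% | 5.1% | 4.4% |
| Equal | 25% | 5.7% | 5.4% | 5.3% | 5.1% | 4.7% | 4.5% |
| Half | 100% | 16.0% | 11.9% | 10.1% | 8.0% | 6.1% | 4.9% |
| Half | 50% | 6.7% | 5.7% | 5.3% | 5.0% | 4.5% | 4.2% |

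With all sessions ordered and K = 3, the equal-variance figure is 17.8% at ICC 0.05 and 21.4% at ICC 0.10.

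**Step 5: a fitted mixed model.** A REML fit with a provider intercept only (400 runs, all ordered, K = 3) reports an SE of 0.126 against an actual 0.194, with type I error 17.5%. If each psychiatrist served only one provider, the error would return to 5.2%.

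**Step 6: binary criterion.** Random-intercept logistic model, 18% in both arms, ICC 0.10, 4,000 null trials per cell:

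- no ordering: 6.3%
- all ordered: 27.7%, 17.9%, 9.6% and 7.5% for K = 2, 4, 10 and 20
- half ordered: 11.0%, 7.5% and 6.8% for K = 2, 4 and 10

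**The case against.** The strongest objection is that the size rests on three inputs the documents do not supply, and that serious inflation needs a small pool, heavy ordering and real psychiatrist variance together. Sharing across providers is inferred from how CL works and is not stated. The psychiatrists get a two-day workshop, three supervised cases and monthly supervision, so they may well differ less than providers do. At a quarter of the provider variance with all sessions ordered, type I error is about 10%, 8%, 7% and 5% for 2, 3, 4 and 10 psychiatrists; with half ordered it is 4% to 5.5%. This stands, and it makes the highest figures an upper corner.

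The wording of Aim 2 refers to providers using MI, which might suggest that CL sessions fall outside H2b. That does not hold: the psychiatrists' sessions are recorded for integrity rating, and the ordering option is what separates ORDER ONE from SEE ONE.

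The standard error would not be too small if conclusions were confined to these particular psychiatrists. But *Study Setting* aims at strategies that other hospitals could adopt, so inference has to reach beyond this pool.

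The conductor may also be recoverable. Each clinician is issued a recorder, and CL experts complete a sleepiness scale for ordered sessions. This largely stands, but no section promises a conductor ID for each recording. The stated requirement is "identifying information that will enable the research assistant to check" the patient's enrolment status, and spare recorders are available on the units.

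Finally, the section describes itself as a general strategy, so an extra random intercept would be compatible with it. That makes the change easy but does not supply the missing term.

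**Conclusion.** The concern holds in conditional form. The planned models omit a conductor component that can cut across providers in ORDER ONE, and the H2b standard error is too small if a few psychiatrists deliver most sessions. With psychiatrist variance equal to provider variance and all sessions ordered, type I error on the continuous score runs from about 26% (2 psychiatrists) to 6% (20). Halving the psychiatrist variance gives 16% to 5%. With a quarter of sessions ordered, or with a large pool, the planned model is close to nominal. The documents do not show which case applies, although the Background presents ordering as simple and low-burden, so heavy use is a plausible result of the strategy. The omission is certain; its size depends on pool size, ordered share and psychiatrist variance. It should be fixed before analysis.

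**What to change.** Make these changes to the SAP and data collection:

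1. Log who conducted each recorded session.
2. For ITRS means, criterion status and change talk, add a random intercept for the conductor alongside the ordering provider. Use Satterthwaite or Kenward-Roger degrees of freedom for continuous outcomes.
3. Conductor and provider coincide in SEE ONE and DO ONE, so state the assumption that conductor variance is equal for providers and psychiatrists. Add a sensitivity analysis with a separate psychiatrist variance in ORDER ONE.
4. Report the number of psychiatrists, the sessions run by each, and the ordered share.
5. Restate H2b power for the expected pool.

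The cost is SAP wording and one data field, plus lower H2b power if the pool is small. With all sessions ordered, ICC 0.07 and d = 0.4:

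| Model | Result | K=2 | 3 | 4 | 10 |
|---|---|---|---|---|---|
| Equal variance | Power | 38% | 51% | 60% | 76% |
| Separate variance | Power | 32% | 38% | 50% | 75% |
| Separate variance | Type I error | 9.4% | 6.2% | 5.0% | 4.9% |

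The comparison figure is 78% when providers run every session. The equal-variance model holds type I error at 5.6% (K = 2) and 4.3% (K = 4), but is conservative if psychiatrist variance is really half (2.3% at K = 3). With half ordered and 4 psychiatrists its power is about 81%. With only 2 psychiatrists a separate variance is poorly estimated, so that sensitivity result needs cautious reading. The lost power reflects information the design lacks in those settings; the planned model would hide the shortfall.

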SECTION VII: RECRUITMENT/CONSENT AND ASSENT PROCEDURES

1. **Targeted Enrollment: Give the number of subjects:**
a. targeted for enrollment at Yale for this protocol __see below__
b. If this is a multi-site study, give the total number of subjects targeted across all sites __n/a__

Participants will be Physician Assistants (PAs) who work at the Yale New Haven Hospital (YNHH) Internal Medicine Hospitalist service and 1200-1600 inpatients who are being cared for by a PA from the Hospitalist Service. All PAs on the Internal Medicine Hospitalist service are eligible to participate. We will obtain written informed consent from all the PAs who express interest in participation and MI training. The PAs will be randomized to one of three conditions that are outlined below. The inpatients who may be eligible subjects will be followed for inpatient care by one of the Internal Medicine hospitalist service PAs. While they will not be randomized, they will follow the randomization condition of their PA. Additionally, we have expanded our target for enrollment to other Healthcare providers (i.e. nursing staff, physician, etc.) who work at Yale New Haven Hospital (YNHH) within general medical inpatient units. Between the PAs and other healthcare providers we intend to enroll 30-40 participants.

2. **Indicate recruitment methods below.** Attach copies of any recruitment materials that will be used.

- | | | |
|--|---|-------------------------------------|
|  Flyers |  Internet/Web Postings |  Radio |
|  Posters |  Mass E-mail Solicitation |  Telephone |
|  Letter |  Departmental/Center Website |  Television |
|  Medical Record Review |  Departmental/Center Research Boards |  Newspaper |
|  Departmental/Center Newsletters |  Web-Based Clinical Trial Registries | |
|  YCCI Recruitment database |  Clinicaltrials.gov Registry (do not send materials to HIC) | |
|  Other (describe): please see below | | |

3. **Recruitment Procedures:**
a. Describe how potential subjects will be identified.
b. Describe how potential subjects are contacted.

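### Table 2: row 1's cells do not multiply to its total (31 x 31 = 961, not 930), and the uptake-adjusted totals 1,116 and 765 follow neither the stated 80% uptake nor any single figure

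*Combined protocol and SAP*

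**What the plan says.** All of this is in the combined protocol and SAP, mainly Section V, item 12, I.2, under the paragraph on adequacy of sample size, and Table 2.

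- **Uptake.** One figure is given: "We estimate 80% of patients across conditions will receive MI". The last column of Table 2 is described as "adjusted for a conservative estimate of MI uptake", but no second uptake figure appears.
- **Table 2, row 1 (continuous outcome).** "d=0.4 300 0.07 31 31 930 1116": effect size, ordinary three-arm total, ICC, providers, patients per provider, unadjusted cluster total, adjusted total.
- **Table 2, row 2 (binary outcome).** "40% vs 18% 195 0.1 30 17 510 765", with the columns in the same order.
- **Number of clusters.** "Feasibility constraints (i.e., 10 Healthcare providers per condition) limited the number of clusters".
- **ICC.** The values "are expected to be small (in the 0.05 to 0.10 range").
- **Conclusion drawn.** "30 Healthcare providers and 40 patients per Healthcare provider will be sufficient for testing the primary hypotheses of the study".

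Section V, item 3 plans 1,200 inpatients. Section VII, item 1 is wider: it gives 1,200 to 1,600 inpatients and says "Between the PAs and other healthcare providers we intend to enroll 30-40 participants".

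**The concern.** Power for the proficiency outcomes depends on the number of recorded MI sessions, not the number of patients enrolled. The uptake adjustment converts one into the other: patients needed equal sessions needed divided by the proportion who receive MI. Both outcomes in Table 2 are rated on the same recorded sessions, so one uptake proportion must serve both rows. The rows use different factors, and neither factor is 1/0.80. In row 1, the provider count, the patients per provider and the total also disagree.

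Table 2 is the only calculation shown in support of 30 providers with 40 patients each. As printed, a reader cannot reproduce row 1 or tell which uptake was assumed. Row 1's adjusted total would also not deliver the sessions that the same row requires at the stated uptake.

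**Working it through.** **1. The plan's figures before adjustment reproduce** (alpha 0.05 two-sided, 80% power, pairwise against control).

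- Row 1, ordinary trial: d=0.4 needs 99 per arm by the normal approximation (297 in three arms) or 100 by the t-test (300). The plan has 300.
- Row 2, ordinary trial: 40% vs 18% needs 65 per arm by the arcsine method (195) or 66 by the pooled normal method (198). The plan has 195.
- Design effect = 1 + (m - 1) x ICC, where m is patients per provider.
  - Row 1: 1 + 30 x 0.07 = 3.1, and 300 x 3.1 = 930.
  - Row 2: 1 + 16 x 0.10 = 2.6, and 195 x 2.6 = 507, rounded up to 30 x 17 = 510.

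The unadjusted totals 930 and 510 are therefore sound.

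**2. Row 1's cells.** 31 x 31 = 961, not 930. With m = 31 the design effect gives 930 = 30 x 31, and the text fixes 10 providers in each of three conditions. Thirty providers is the most likely reading. It remains an inference, because 31 x 30 is also 930.

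**3. Uptake adjustment.** Patients = sessions / uptake.

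| | Row 1 | Row 2 |
|---|---|---|
| Sessions needed | 930 | 510 |
| Printed adjusted total | 1,116 | 765 |
| Factor used (printed / sessions) | 1.20 | 1.50 |
| Implied uptake (sessions / printed) | 83.3% | 66.7% |
| Correct at 80% | 930 / 0.8 = 1,162.5, so 1,163 | 510 / 0.8 = 637.5, so 638 |
| Printed minus correct | -47 | +127 |
| Sessions from printed total at 80% | 892.8, so 893 (37 short) | 612 (102 over) |

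Row 1 looks like a multiplication by 1 + 0.20 in place of a division by 0.80. The same slip in row 2 would give 510 x 1.2 = 612, not 765. No single uptake yields both printed totals, by division or by multiplication.

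**4. Planned enrolment.** 1,200 x 0.80 = 960 sessions, which meets both 930 and 510.

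**5. Dependence on the ICC (a qualification, not an arithmetic error).** Take 32 sessions per provider (80% of 40), k providers per arm, d=0.4 and two-sided 0.05. The standardised difference is d / sqrt(2 x (1 + 31 x ICC) / (32k)). The plan names no reference distribution, so both are shown.

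| Providers per arm | Reference | ICC 0.05 | ICC 0.07 | ICC 0.10 |
|---|---|---|---|---|
| 10 | Normal | 88.7% | 81.1% | 70.5% |
| 10 | t, 27 df | 86.3% | 78.2% | 67.3% |
| 13 | Normal | 95.1% | 90.0% | 81.3% |
| 13 | t, 36 df | 94.0% | 88.3% | 79.2% |

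Thirteen per arm is 39 providers, within the 30 to 40 of Section VII, item 1. With 10 per arm, power is exactly 80% at an ICC of 0.073 (normal) or 0.066 (t). With 10 per arm and ICC 0.10, normal-approximation power is 87.8% for d=0.5 and 86.5% for 40% vs 18%.

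**6. Scope of Table 2.** The sources cited for d, and the 40% vs 18% comparison on the MI performance criterion, concern how well MI is delivered. The table has no assumed uptake rates by arm, so it contains no calculation for H1a or H1b.

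**The case against.** The strongest reply is that nothing in the conduct of the trial changes. The 31 in row 1 is one cell, perhaps a typing slip or a fault in reading the table from PDF, and the rest of the page points to 30. The shortfall in row 1 hardly affects power: 893 sessions over 30 providers (about 29.8 each) give 80.3% for d=0.4 at ICC 0.07 by the normal approximation, against 80.7% at 31 each. Enrolment is set at 1,200, not 1,116, and row 2 errs on the safe side. The ICC used is printed in the table and its range is in the text. The 70% figure also pairs the smallest cited effect with the largest ICC, although the plan expects at least medium effects.

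Much of this stands. The consequence is limited, the 30-provider reading is recoverable, and the ICC point is a matter of disclosure. Two parts do not stand. First, the adjusted totals are wrong however the provider cell is read. Second, an unstated conservative uptake cannot explain them: row 1's implied 83.3% is less conservative than 80%, and two different uptakes cannot apply to outcomes scored on the same sessions.

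**Conclusion.** The concern holds. Row 1's cells conflict as printed (961 against 930), and both adjusted totals are wrong for the only stated uptake: 1,116 is 47 too low against 1,163, and 765 is 127 too high against 638. These corrections take 930 and 510 as correct, which the plan's own inputs support, and 80% as the intended uptake.

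The planned 1,200 covers both corrected totals. Its margin over row 1 is 37 patients (1,200 - 1,163), not the 84 (1,200 - 1,116) that the table suggests. Only if 31 providers with 31 sessions each were truly required would the need pass 1,200, and then barely: 961 / 0.8 = 1,201.25, so 1,202.

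Power clearly below 80% for d=0.4 arises only towards the top of the stated ICC range and at the lower end of the provider target. No deficit is claimed for H1a or H1b; the sufficiency statement simply goes beyond what Table 2 calculates.

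**What to change.** - Reconcile row 1's provider, patient and total cells, most likely to 30 providers x 31 = 930.
- State one uptake figure and divide both rows by it. At 80% the totals are 1,163 and 638. If a lower, conservative figure was intended, state it, apply it to both rows and check the results against 1,200.
- Say that 80% power for d=0.4 is conditional on an ICC of about 0.07. Naming the reference distribution and showing power at ICC 0.05, 0.07 and 0.10, for 30 providers and for any larger number enrolled, would be a useful addition.
- Limit the sufficiency sentence to the proficiency outcomes in Table 2, or add a calculation for H1a and H1b with the assumed uptake in each arm.

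The cost is a correction to one table and a few sentences. At 80% uptake it needs no added enrolment.
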